To assess their eligibility to enter the study, potential subjects will be screened within 28 days (Days -29 to -2) and be admitted to the Clinical Research Unit (CRU) on Day -1 (Check-in).

Subjects will be confined at the CRU from the time of Check-in (Day -1) until End of Treatment (EOT) on Day 16 upon completion of all PK and safety assessments or Early Termination (ET) if the subject discontinues. A follow-up phone call will occur for all subjects who received at least 1 dose of study drug (including subjects who are terminated early) 7 days (± 2 days) after EOT or ET.

Replacement subjects may be enrolled only if deemed necessary by the Sponsor.

The start of the study is defined as the date the first subject who is enrolled in the study signs an Informed Consent Form. Note that enrolled subjects are defined as those subjects who are assigned a dose of study drug; this definition excludes screen failure subjects. Study completion is defined as the time of the last subject's follow-up.

In this study, physical examinations, 12-lead electrocardiograms (ECGs), vital sign measurements, How Do You Feel? inquiries, clinical chemistry panel, coagulation parameters, hematology panel, urinalysis (UA; Appendix 2), and recording of concomitant medications will be performed at specified times during the study (for specific timepoints and details on each study variable, refer to Appendix 4).

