# 4.6. Removal of Subjects from Study Participation

Subjects will be informed that they are free to withdraw from the study at any time and for any reason. The Investigator (or designee) may remove a subject from the study if, in the Investigator's (or designee's) opinion, it is not in the best interest of the subject to continue the study. Subjects may be withdrawn because of the following:

 change in compliance with inclusion/exclusion criterion that is clinically relevant and affects subject safety

- occurrence of AEs
- occurrence of pregnancy
- non-compliance with study restrictions

Notification of withdrawal will immediately be made to the Sponsor. In case of withdrawal, efforts will be made to perform all final study day assessments (Appendix 4). The date the subject is withdrawn from the study and the reason for withdrawal will be recorded on the subject's electronic Case Report Form (eCRF). All withdrawn subjects with AEs that are assessed as related to study drug and which are ongoing at ET may continue to be followed until the symptoms or value(s) return to normal, or acceptable levels, as judged by the Investigator (or designee) and confirmed by the Sponsor.

The entire study may be discontinued at the discretion of the Investigator (or designee) or Sponsor, based on the occurrence of the following:

- AEs unknown to date with respect to their nature, severity, and/or duration;
- increased frequency and/or severity and/or duration of known AEs;
- medical or ethical reasons affecting the continued performance of the study;
- difficulties in the recruitment of subjects;
- cancellation of drug development.

In the event that the study is terminated early, the Sponsor or its designee will provide specific guidance to the CRU regarding the EOS procedures.

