# **Appendix 4: Schedule of Assessments**

			Period 1	Period 2											Clinic Discharge/ EOT/ET u	Follow-up Phone Call (EOS)			
Study Procedures a	Screening (Days -29 to -2)	(Day -1)	1	2	3	4	5	6	7	8	9	10	11	12	13	14	15	16	7 (± 2) days post EOT/ET w
Confined to the CRU		X	X	X	X	X	X	X	X	X	X	X	X	X	X	X	X	X	
Inclusion/Exclusion Criteria	X	X																	
Informed Consent	X																		
Demographics	X																		
Medical History	X	Xb																	
Height/Weight/BMI	Xc	Xc																	
eGFR	X	X																	
Physical Examination d		X																X	
12-lead ECG e	X	X	X	X				X						X				X	
Vital Sign Measurements f	$X^{g,h}$	$X^{g,h}$	$X^h$	X				X						X				$X^{g,h}$	
HDYF? Inquiryi	X	X	X	X	X	X	X	X	X	X	X	X	X	X	X	X	X	X	X
AEs/SAEs j	X	X	X	X	X	X	X	X	X	X	X	X	X	X	X	X	X	X	X
Repaglinide Dosing k			X											X					
LOXO-305 Dosing 				X	X	X	X	X	X	X	X	X	X	X					
CCI																			
Clinical Laboratory Evaluations o	X	X		X				X					X		X		X v	X v	
Hepatitis and HIV Screen	X																		
COVID-19 Test p	X	X																	
HbA1c Test	X																		
Drug Screen q	X	X																	
Prior and Concomitant Medications r	X	X	X	X	X	X	X	X	X	X	X	X	X	X	X	X	X	X	X
Serum Pregnancy Tests	X	X															X v	X v	
FSH Test t	X																		

Covance Study: 8425120 Protocol Reference: LOXO-BTK-20016

		Period 1														Clinic Discharge/ EOT/ET u	Follow-up Phone Call (EOS)	
Study Procedures a	Screening (Days -29 to -2)		2	3	4	5	6	7	8	9	10	11	12	13	14	15	16	7 (± 2) days post EOT/ET w
TSH Test	X																	

Abbreviations: AE = adverse event; BMI = body mass index; BP = blood pressure; COVID-19 = SARS-CoV-2; CRF = Case Report Form; CRU = Clinical Research Unit; ECG = electrocardiogram; eGFR= estimated glomerular filtration rate; EOS = End of Study; EOT = End of Treatment; ET = Early Termination; FSH = follicle-stimulating hormone; HbA1c = hemoglobin A1c; HDYF? = How Do You Feel?; HIV = human immunodeficiency virus; ICF = Informed Consent Form PK = pharmacokinetic; QD = once daily; SAE = serious adverse event; TSH = thyroid-stimulating hormone; UA = urinalysis.

- a. For details on study procedures, see Section 7.
- b. Interim medical history only.

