- j. AEs and SAEs will be collected beginning at informed consent. AEs will be recorded throughout the study (ie, from signing of the ICF until EOS, or until ET if the subject discontinues from the study and does not complete a follow-up phone call), either as subject medical history (if the event is reported as beginning prior to signing of the ICF or if the event occurs prior to study drug administration on Day 1 and is assessed as not related to study procedures by the Investigator [or designee]) or as AEs (if the event occurs after signing of the ICF but prior to study drug administration on Day 1 and is assessed by the Investigator [or designee]) as related to study procedures, or if the event occurs after study drug administration on Day 1 through EOT or ET regardless of relationship to study drug). From EOT or ET through EOS, only AEs assessed as related to study drug are to be recorded. All SAEs that develop from the time of ICF signing until EOS (or ET if the subject discontinues from the study and does not complete a follow-up phone call) are to be reported.
- k. On Day 1, repaglinide will be administered in the morning following a fast of 10 hours prior to dosing and subjects will receive a standardized light breakfast (examples of contents are detailed in Table 4) 15 minutes post-repaglinide dose. On Day 12, 200 mg LOXO-305 and 0.5 mg of repaglinide will be co-administered at the same time in the morning at the actual time of the Day 1 repaglinide dose (± 1 hour), following a fast of 10 hours prior to dosing and subjects will receive a standardized light breakfast (examples of contents are detailed in Table 4) 15 minutes post LOXO-305 and repaglinide dosing.

Covance Study: 8425120 Prot

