1. On Days 2 through 11, oral doses of 200 mg LOXO-305 will be administered QD in the morning at the actual time of the Day 1 repaglinide dose (± 1 hour). On Days 2 through 11, subjects will be fasted for at least 2 hours predose and 1 hour postdose (with the exception of days where clinical laboratory evaluations are performed [Day 2, Day 6, and Day 11, where subjects are fasted for 8 hours predose and 1 hour postdose]). On Day 12, 200 mg LOXO-305 and 0.5 mg of repaglinide will be co-administered in the morning at the actual time of the Day 1 repaglinide dose (± 1 hour), following a fast of 10 hours prior to dosing and subjects will receive a standardized light breakfast (examples of contents are detailed in Table 4) 15 minutes post-LOXO-305 and repaglinide dosing.

to be fasted prior to clinical laboratory evaluations.

- p. Testing for COVID-19 will be conducted at a minimum at Screening and Check-in (Day -1). Testing for COVID-19 may also be conducted periodically during the subject's CRU confinement, at the discretion of the Investigator (or designee). Tests will be performed by rapid polymerase chain reaction or equivalent.
- q. Drugs of abuse urine test, including cotinine and alcohol. Results from the drugs of abuse tests will be used to determine subject eligibility per the inclusion/exclusion criteria.
- r. Prior and concomitant medication administration will be recorded beginning at informed consent. In addition, all Investigator-approved medications taken by a subject within 14 days, or 5 half lives (if known), whichever is longer, prior to Day 1 for prescription medications and over-the-counter medication, will be recorded on the subject's electronic CRF.
- s. Female subjects only.
- t. Post-menopausal female subjects only.

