- u. The EOT is defined as when the subject is released from the CRU following completion of all assessments through Day 16 (EOT) or ET. The ET is defined as when the subject is released from the CRU if the subject terminates the study early. Vital sign measurements, ECG, and abbreviated physical examination results are to be available for review by the Investigator (or designee) prior to subject release from the CRU at the EOT visit. Clinical laboratory evaluation results for clinical chemistry, hematology, coagulation, and UA and serum pregnancy test results (female subjects only) are to be available for review by the Investigator (or designee) prior to subject release from the CRU at the EOT visit and prior to subject release from the CRU at the ET visit, if available.
- v. Clinical laboratory evaluations and serum pregnancy test (female subjects only) will be performed on the day prior to subject release from the CRU (Day 15) if the subject completes the study (EOT). Clinical laboratory evaluations and serum pregnancy test (female subjects only) will be performed on the day of subject release from the CRU if the subject terminates early (ET).
- w. To be conducted 7 days (± 2 days) following EOT (Day 16) or ET. The EOS is defined as when the subject is contacted by the CRU for a follow-up phone call 7 days (± 2 days) after the EOT visit or ET visit to determine if any SAE or study drug-related AE has occurred since the EOT or ET visit. All subjects who received LOXO-305 (including subjects who are terminated early) will receive a follow-up phone call.

z. Denotes predose sample collection only.

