There will be a washout period of 11 days between the dose of repaglinide on Day 1 and the dose of repaglinide on Day 12, respectively.

To assess their eligibility to enter the study, potential subjects will be screened within 28 days (Days 29 to -2) and be admitted to the Clinical Research Unit (CRU) on Day -1 (Check in).

Subjects will be confined at the CRU from the time of Check in (Day -1) until end of treatment (EOT) on Day 16 upon completion of all PK and safety assessments or Early Termination (ET) if the subject discontinues. A follow up phone call will occur for all subjects who received at least 1 dose of study drug (including subjects who are terminated early) 7 days (± 2 days) after EOT or ET. The duration of participation is expected to be approximately 54 days (Screening through follow up phone call).

Replacement subjects may be enrolled only if deemed necessary by the Sponsor.

The start of the study is defined as the date the first subject who is enrolled in the study signs an Informed Consent Form (ICF). Note that enrolled subjects are defined as those subjects who are assigned a dose of study drug; this definition excludes screen failure subjects.

In this study, physical examinations, 12 lead ECGs, vital sign measurements, How Do You Feel? inquiries, clinical chemistry panel, coagulation parameters, hematology panel, urinalysis, and recording of concomitant medications will be performed at specified times during the study.

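### Does Appendix 4 footnote w leave subjects who took only repaglinide without the safety follow-up call?

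*Protocol*

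**What the plan says.** Four statements say who receives the follow-up call by reference to a drug or dose.

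- Protocol Synopsis, Study Design: "A follow-up phone call will occur for all subjects who received at least 1 dose of study drug". Protocol Section 3.1 says the same.
- SAP Section 4: "A follow up phone call will occur for all subjects who received at least 1 dose of study drug".
- Protocol Appendix 4, footnote w, last sentence: "All subjects who received LOXO-305 (including subjects who are terminated early) will receive a follow-up phone call".

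Study drug means repaglinide, LOXO-305 or both. Protocol Section 8.2.1 and SAP Section 7.2 spell this out in defining the Safety Population, and protocol Table 3 lists both products.

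Footnote w also ties the end of study to the call: "The EOS is defined as when the subject is contacted by the CRU for a follow-up phone call". The column for the call is headed "7 (± 2) days post EOT/ET". Protocol Section 7.2.1 states the call for subjects generally, with the same timing and with no condition on which drug was taken.

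On the reporting period, Appendix 4 footnote j has SAEs that develop "until EOS (or ET if the subject discontinues from the study and does not complete a follow-up phone call) are to be reported".

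**The concern.** Repaglinide is given alone on Day 1, and LOXO-305 starts on Day 2. A subject who leaves between the two has had study drug, belongs to the Safety Population, and is owed a call under the Synopsis, Section 3.1 and SAP Section 4. The last sentence of footnote w does not name that subject.

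The place of the sentence gives it some weight, because site staff work from the Schedule of Assessments. Section 4.6 also points there for withdrawn subjects: "In case of withdrawal, efforts will be made to perform all final study day assessments (Appendix 4". If a site took the sentence as the full rule and made no call, footnote j could be read as closing event collection at early termination. SAEs and drug-related AEs would then be collected for a shorter time in that subject than in the rest of the Safety Population.

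**Working it through.** The plan gives no figure to reproduce. The check sets the passages side by side and then sizes the worst case.

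**Who falls between the wordings.** Group A is everyone who had repaglinide and/or LOXO-305 (Synopsis, Section 3.1, SAP Section 4). Group B is everyone who had LOXO-305 (footnote w, last sentence). B lies inside A. The difference is subjects dosed with repaglinide on Day 1 who never take LOXO-305.

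**Whether any instruction conflicts.** For such a subject:

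| Place | Does it call for the follow-up call? |
|---|---|
| Protocol Synopsis and Section 3.1 | Yes |
| SAP Section 4 | Yes |
| Protocol Section 7.2.1 | Yes; no drug condition |
| Footnote w, timing sentence and end-of-study definition | Yes; no drug condition |
| Appendix 4 column heading | Yes; applies after any EOT or ET |
| Footnote w, last sentence | Silent; says B is called, not that only B is called |

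No row forbids the call, and five of the six require it or cover the subject. Footnote a, attached to the procedures heading of the same table, sends the reader to Section 7 for details, and Section 7.2.1 holds the unrestricted instruction.

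**Size if a site nonetheless skipped the call.**

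- Time from the Day 1 repaglinide dose to the first LOXO-305 dose. LOXO-305 "will be administered QD in the morning at the actual time of the Day 1 repaglinide dose (± 1 hour", so the interval is 24 − 1 = 23 h to 24 + 1 = 25 h.
- Collection after early termination that depends on the call: 7 − 2 = 5 days to 7 + 2 = 9 days.
- Assume release no later than 25 h after the Day 1 dose (25/24 ≈ 1.0 day). Post-dose collection is then at most about 1.0 day without the call. With it, collection runs up to 1.0 + 5 = 6.0 days or 1.0 + 9 = 10.0 days, depending on when the call falls in its window.

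The 1.0-day figure rests on that release assumption. A subject whose Day 2 dose was withheld could be kept in the unit longer, which Section 7.2.1 allows, and collection would continue during the stay.

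**Effect on the analyses.** The PK Population requires a LOXO-305 dose (protocol Section 8.2.1, SAP Section 7.3), so these subjects are outside it in any case. Membership of the Safety Population depends on dosing and not on the call. Safety results are descriptive only (SAP Section 8.6.6).

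**The case for a change.** The best case for an edit is that a sentence whose only job is to say who gets the call should name the same group as its three counterparts. Footnote w also sits badly with itself: the sentence before gives the purpose of the call as finding SAEs and events related to study drug, which includes repaglinide. An exit in the gap is foreseeable, since AEs are a listed reason for withdrawal (Section 4.6) and Section 1.6 names hypoglycemia as a possible side effect of repaglinide. Section 7.2.1 requires follow-up to the end of study but makes an exception for a withdrawn subject who does not complete the call, so that requirement alone would not rescue a call that was never placed.

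The inconsistency in wording stands. The route from it to lost data is weak:

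- The exceptions in Section 7.2.1 and footnote j most naturally describe a subject who cannot be reached or declines. They do not naturally describe a site leaving out a call that other sections require.
- Section 7.2.1 does more than state an exception. It separately requires the call, with no drug condition.
- The Section 4.6 pointer concerns final study day assessments. That reads most naturally as the Day 16 EOT/ET column, while the call has its own later column.
- Related AEs still ongoing at early termination may be followed further under Section 4.6. Only new SAEs or new related AEs in the 5 to 9 days would be at stake.

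**Conclusion.** The concern calls for no change to the plan. One sentence of footnote w names a narrower group than the Synopsis, Section 3.1 and SAP Section 4. It does so without excluding anyone, and a site that follows the whole protocol already calls every dosed subject. Aligning the phrase would be harmless tidying, but it would alter no required procedure, population, endpoint or analysis.

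A loss would need three things together: a subject leaving before any LOXO-305 dose, a site reading one sentence as exclusive against the other passages, and a new SAE or drug-related AE within 5 to 9 days of early termination. The documents give no expected rate for such early exits. That few or none of up to 16 subjects would be affected is a judgement from the shortness of the 23 to 25 hour gap. The conclusion also rests on reading the footnote together with Section 7.2.1, as footnote a directs.

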#### LIST OF ABBREVIATIONS

Abbreviations pertain to the statistical analysis plan (SAP) only (not the tables, figures, and listings [TFLs]).

ADaM analysis data model

AE adverse event

AUC area under the concentration-time curve

AUC0-inf area under the concentration-time curve from time 0 extrapolated to

infinity

 $AUC_{0-t}$  area under the concentration-time curve from hour 0 to the last

measurable concentration

%AUCextrap percentage extrapolation for area under the concentration-time curve

extrapolated to infinity

BLQ below the limit of quantification

CDISC Clinical Data Interchange Standards Consortium

CI Confidence interval

CL/F apparent systemic clearance

CLss/F apparent systemic clearance at steady state

Cmax maximum observed concentration

COVID-19 SARS-CoV-2

Ctrough concentration observed at the end of the dosing interval

CRU Clinical Research Unit
CSR clinical study report

CTCAE Common Terminology Criteria for Adverse Events

CV coefficient of variation ECG electrocardiogram

EOS end of study
EOT end of treatment
ET early termination
Geom CV Geometric CV
Geom Mean Geometric mean

ICF informed consent form

ICH International Council for/Conference on Harmonisation of Technical

Requirements for Registration of Pharmaceuticals for Human Use

 $\lambda_{\rm Z}$  apparent terminal elimination rate constant

ln natural log

LSM Least squares mean

MedDRA Medical Dictionary for Regulatory Activities

NC not calculated

PK pharmacokinetic(s)

QD once daily

SAE serious adverse event
SAP statistical analysis plan
SD standard deviation

 $t_{1/2}$  apparent terminal elimination half-life TEAE treatment-emergent adverse event

TFL table, figure, and listing

tmax time to maximum observed concentration

 $V_z/F$  apparent volume of distribution at terminal phase WHODrug World Health Organization Drug Dictionary

#### 1. INTRODUCTION

This SAP has been developed after review of the clinical study protocol (Final Version 1.0 dated 05 October 2020) and electronic case report form.

This SAP describes the planned analysis of the pharmacokinetic (PK) and safety and tolerability data from this study. A detailed description of the planned TFLs to be presented in the clinical study report (CSR) is provided in the accompanying TFL shells document.

In general, the analyses are based on information from the protocol, unless they have been modified by agreement with Loxo Oncology, Inc. A limited amount of information about this study (eg, objectives, study design) is given to help the reader's interpretation. This SAP must be finalized prior to the lock of the clinical database for this study. When the SAP and TFL shells are approved, they will serve as the template for this study's CSR.

This SAP supersedes any statistical considerations identified in the protocol; where considerations are substantially different, they will be so identified. If additional analyses are required to supplement the planned analyses described in this SAP, they may be performed and will be identified accordingly in the CSR. Any substantial deviations from this SAP will be agreed with Loxo Oncology, Inc. and identified in the CSR.

This SAP is written with consideration of the recommendations outlined in the International Conference on Harmonisation (ICH) E9 guideline *Statistical Principles for Clinical Trials* and ICH E3 guideline *Structure and Content of Clinical Study Reports*. 

The document history is presented in Appendix 1.

#### 2. STUDY OBJECTIVES

#### 2.1. Primary Objective

The primary objective of the study is:

• to assess the impact of multiple oral doses of LOXO-305 on the PK of a single oral dose of repaglinide (CYP2C8 substrate) in healthy subjects.

# 2.2. Secondary Objective

The secondary objective of the study is:

• to assess the safety and tolerability of multiple oral doses of LOXO-305 when administered alone and coadministered with repaglinide in healthy subjects.

#### 3. STUDY ENDPOINTS

#### 3.1. Primary Endpoints

The following PK parameters will be calculated, whenever possible, based on the plasma concentrations of repaglinide following single oral dose administration (as appropriate):

• area under the concentration-time curve from hour 0 to the last measurable concentration (AUC0-t)

- area under the concentration-time curve from hour 0 extrapolated to infinity (AUC0-inf)
- percentage extrapolation for AUC0-inf (%AUCextrap)
- maximum observed plasma concentration (Cmax)
- time to maximum concentration (tmax)
- apparent terminal elimination rate constant  $(\lambda_Z)$
- apparent systemic clearance (CL/F)
- apparent terminal elimination half-life  $(t_{1/2})$
- apparent volume of distribution  $(V_z/F)$ .

The following PK parameters will be calculated whenever possible, based on the plasma concentrations of LOXO-305 following multiple dose administration (as appropriate):

- AUC0-t
- AUC during a dosing interval (AUCtau)
- Cmax
- concentration observed at the end of the dosing interval (Ctrough)
- tmax
- CL/F at steady state (CLss/F).

